# 2.4 Sample Size Calculations

# 2.5 Interim Analysis

No formal interim analyses are planned for this study. As such, no formal statistical rule for early termination of the trial is defined. Interim study reports with descriptive analysis may be produced for regulatory or reimbursement purposes.

# 2.6 Timing of Analysis

Analysis of the primary endpoint and other endpoints will occur once all subjects have either completed the 1-month follow-up or withdrawn from the study.

# 2.7 Study/Trial Success

The clinical investigation is successful if the primary endpoint is met for both the lead-only configuration group and the full DBS system group.

# 2.8 **Subgroups for Analysis**

No subgroup analyses are planned for this clinical investigation.

# 2.9 Handling of Missing Data

No imputation techniques will be implemented in the analysis. The secondary endpoints will be evaluated in subjects who undergo an MRI procedure with a full system configuration. Subjects who don't have the IPG testing complete immediately after MRI procedure will be excluded from the related endpoint analysis.

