5.8 Number of Subjects

To support the safety of the Infinity DBS system with MR Conditional labeling, up to 74 subjects will be enrolled in this study. Approximately 35 subjects will be included in each device configuration group (Leads Only and Full System). The total number of enrolled subjects assumes a 5% attrition rate following enrollment (e.g., due to subject unwilling to undergo DBS implant procedure, or for any other reason). Data from only one MRI procedure for each subject will be collected.

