6.3.2 Immediate Post-MRI Procedure (In clinic, after the MRI procedure has been performed)

The following data will be collected after the MRI procedure:

- MRI scanner manufacturer/model
- Scan region (anatomic location)
- Subject position during MRI procedure
- Static field strength
- RF coil type
- RF power
 - o B1+RMS, head SAR, and/or whole body SAR, if applicable
 - Duration of each scan
- Total active scan time
- DICOM image files (de-identified), if available
- Adverse events
- Protocol deviations (if applicable)
- Withdrawal (if applicable)
- Device deficiency (if applicable)
- Product out of service (if applicable)

For subjects in the full system configuration group, the following additional data will be collected immediately after the MRI procedure:

- Success or failure of 'turn off' functionality of MRI mode
- Success or failure to 'turn on/off' functionality of the stimulation
- Success or failure to make adjustments to the stimulation amplitude
- Success or failure of device interrogation and download of IPG parameters Success or failure to obtain lead impedance measurements (only if the Clinician Programmer is being used to interrogate the IPG)

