6.4.4 Schedule of Events

CIP Activity	Enrollment	Baseline	MRI visit		1 Month post-MRI Follow-	Unscheduled
			Pre-MRI/ MRI Procedure	Immediate Post- MRI Procedure	up (30 days ± 14 days after MRI procedure)	
Informed Consent Process	X					
Inclusion/Exclusion Criteria Check	X					
Demographics		X				
Medical condition indicated for MRI procedure		X				
Subject eligibility for MRI procedure			X			
Medical indication for DBS		X				
DBS Lead information			X			(X)
IPG and extension information			X*			(X)
MRI procedure			X			
DICOM image files				(X)		
MRI parameters				X		
Turn "on" of MRI mode			X*			
Turn "off" of MRI mode				X*		
"On/off" of stimulation			X*	X*	X**	
Adjustments to the stimulation amplitude			Х*	X*	X**	
Interrogation and download of IPG parameters			Х*	X*	X**	
Impedance testing			(X*)	(X*)	(X**)	
Session records			(X*)	(X*)	(X**)	(X**)
Adverse Events	(X)	(X)	(X)	(X)	(X)	(X)
Protocol Deviation	(X)	(X)	(X)	(X)	(X)	(X)
Withdrawal	(X)	(X)	(X)	(X)	(X)	(X)
Product Out of Service Data	(X)	(X)	(X)	(X)	(X)	(X)
Device Deficiency Information	(X)	(X)	(X)	(X)	(X)	(X)

X* = for subjects in the full system configuration group

X** = for subjects with a full DBS system implant (includes subjects in the full system configuration group and subjects in the leads-only group who had an IPG implanted and connected to at least one lead after the MRI procedure)

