8.2.2 Secondary Endpoint Analysis

The following secondary endpoints will be analyzed for subjects who undergo an MRI procedure with a full system configuration. The endpoint "Rate of successful ability to obtain lead impedance measurements" will include only those subjects who had their IPG interrogated using the Clinician Programmer. Data (success or failure) for these endpoints will be collected immediately after the MRI procedure.

- Rate of successful MRI mode 'turn on/off' functionality of the MRI mode
- Rate of successful 'turn on/off' functionality for the stimulation
- Rate of successful adjustments to the stimulation amplitude
- Rate of successful interrogation and download of the IPG parameters
- Rate of successful ability to obtain lead impedance measurements

Rates will be reported as the percentage of subjects in which the device functionality could be successfully completed.

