#### 2.2.2 **Descriptive Statistics for Categorical Variables**

For categorical variables, results will be summarized with subject counts and percentages/rates, and where specified in the table mockups, with exact 95% Clopper-Pearson confidence intervals.

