# 2.3.2 Secondary Endpoints

The following secondary endpoints will be analyzed for subjects who undergo an MRI procedure with a full system configuration. The endpoint "Rate of successful ability to obtain lead impedance measurements" will include only those subjects who had their IPG interrogated using the Clinician Programmer. Data (success or failure) for these endpoints will be collected immediately after the MRI procedure.

- Rate of successful MRI mode 'turn on/off' functionality of the MRI mode
- Rate of successful 'turn on/off' functionality for the stimulation
- Rate of successful adjustments to the stimulation amplitude
- Rate of successful interrogation and download of the IPG parameters
- Rate of successful ability to obtain lead impedance measurements

Rates will be reported as the percentage of subjects in which the device functionality could be successfully completed.

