# 2.11 Multiplicity Issues

Since there is no hypothesis testing in this study, no multiplicity adjustment will be considered.

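### SAP 2.9 excludes incomplete post-MRI IPG tests whatever the cause, so a dependent function left untested because of a device fault drops out of its own success rate

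*SAP*

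**What the plan says.** The secondary endpoints are five device-function rates in subjects scanned with a full system: MRI mode on/off, stimulation on/off, amplitude adjustment, interrogation with parameter download, and lead impedance.

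- **Definition.** SAP 2.3.2 states: "Rates will be reported as the percentage of subjects in which the device functionality could be successfully completed". Protocol 8.2.2 uses the same definition. Both take the data from the check made straight after the scan.
- **Data capture.** Protocol 6.3.2 records each function as a binary outcome, for example "Success or failure to make adjustments to the stimulation amplitude". The Schedule of Events (Protocol 6.4.4) marks the post-MRI function tests "X* = for subjects in the full system configuration group". Impedance is tested only where the Clinician Programmer is in use.
- **Missing data.** SAP 2.9 rules out imputation and adds that subjects who do not "have the IPG testing complete immediately after MRI procedure will be excluded from the related endpoint analysis". Protocol 8.6 also rules out imputation but contains no such exclusion.
- **Back-up analyses.** SAP 2.13 plans no sensitivity analysis.
- **Role of these rates.** Success depends on the primary endpoint alone (SAP 2.7, Protocol 8.9). SAP 2.11 adds: "Since there is no hypothesis testing in this study, no multiplicity adjustment will be considered".

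**The concern.** The functions are linked in practice. If the programmer cannot communicate with the IPG after the scan, a site may record the failed interrogation and then not attempt the remaining steps. Those later tests are incomplete because of the kind of fault the endpoints exist to detect, so the missingness is informative.

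SAP 2.9 treats such a case in the same way as a test skipped because the clinic ran out of time: the subject is removed from that endpoint. An excluded subject of this kind could not have contributed a success, so the exclusion can only leave the reported rate unchanged or raise it.

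What is at stake is the accuracy of a descriptive safety table that goes to the notified body. In a group of about 35, one subject decides whether a line reads 100%.

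**Working it through.** **Which cases are affected.** There are three ways a function can fail to be a recorded success after the scan.

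1. It was attempted and failed. Protocol 6.3.2 records a failure, and the subject stays in the denominator. No problem.
2. It was not tested for a reason unrelated to the device. SAP 2.9 excludes the subject from that endpoint. This is reasonable.
3. It was not tested because a device or communication fault blocked it. SAP 2.9 as written excludes the subject. The definition in SAP 2.3.2 and Protocol 8.2.2 points to not completed. No passage says how to score this case.

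Only the third case matters here.

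**Inputs.**
- Full-system group size n: about 35 (Protocol 5.8).
- Check on that figure: two groups of 35 give 70, and with 5% attrition 70/0.95 = 73.7, which rounds up to the stated 74. So 35 is the size after attrition. Half of 74 is 37.
- k, the number of subjects in case 3 for a given function: not in the documents, so assumed.
- f, the number of recorded failures: assumed 0 unless stated.

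**Formulas.**
- As written: (n − k − f)/(n − k)
- Case 3 counted as not completed: (n − k − f)/n
- Difference when f = 0: 1 − (n − k)/n = k/n

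**Results at n = 35, f = 0.**

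| k (assumed) | As written | Counted as not completed | Overstatement |
|---|---|---|---|
| 0 | 35/35 = 100% | 35/35 = 100% | 0 |
| 1 | 34/34 = 100% | 34/35 = 97.1% | 2.9 points |
| 2 | 33/33 = 100% | 33/35 = 94.3% | 5.7 points |
| 3 | 32/32 = 100% | 32/35 = 91.4% | 8.6 points |

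**Sensitivity to the assumptions.**
- n from 30 (assumed) to 37: for k = 1 the overstatement runs from 1/30 = 3.3 to 1/37 = 2.7 points; for k = 3, from 3/30 = 10.0 to 3/37 = 8.1 points.
- One recorded failure as well (f = 1, k = 1, n = 35): 33/34 = 97.1% against 33/35 = 94.3%, a difference of about 2.8 points.
- Impedance has a smaller denominator, which the documents do not give. With an assumed 20 subjects, k = 1 gives 19/19 = 100% against 19/20 = 95.0%.

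Confidence limits are left out because SAP 2.2.2 plans them only "where specified in the table mockups, with exact 95% Clopper-Pearson confidence intervals", and the mockups are not in the public copy.

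**The case against.** The best reply is that SAP 2.9 concerns missing data, whereas a device that does not respond has given an observed result. Protocol 6.3.2 asks for success or failure, so a site facing an unresponsive IPG should record failure on each function, and nothing would be missing. On that reading the definition governs failures, the exclusion governs absent data, and the two fit together.

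Much of this stands. A reader might infer that SAP 2.3.2 and SAP 2.9 contradict each other outright, or that every device failure vanishes from the table. The documents do not support either reading, because attempted failures are kept. The CRF is also not shown; it may force a success-or-failure entry or already ask why a test was not done, and then the gap could close in practice. What remains is that no rule in the documents tells a site to score a blocked, unattempted test as a failure. Sites could code the same event differently, and a blank entry leads to exclusion.

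A second reply is that the fault would still be seen elsewhere: as a failed interrogation, as a device deficiency (Protocol 7.4.2), or in the repeat tests at 1 month (Protocol 6.4.1). The first two are genuine routes, so a reader should not infer that the fault goes unrecorded. They do not correct the rate for the dependent function. The 1-month tests do not feed these endpoints, which use the immediate post-MRI data, and MRI mode is not among the functions retested then.

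A third reply is that k is assumed. That is correct: nothing in the documents suggests that k would be 2 or 3, and it may well be 0.

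**Conclusion.** The point holds in a limited form and is of low priority. SAP 2.9 states an exclusion with no condition on cause. Applied as written, it removes from a function's denominator any subject whose test was blocked by a device or communication fault. Each such case overstates that rate by about 1/n, or 2.9 points at n = 35, and the error cannot go the other way.

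This rests on three assumptions: that at least one such case occurs, that the site leaves the dependent test blank instead of recording a failure, and that the CRF does not prevent a blank.

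A reader might infer that the study's conclusion is at risk. It is not: success rests on the primary endpoint in both configuration groups, and the secondary rates carry no threshold or test.

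**What to change.** Add to SAP 2.9, before the data are analysed, wording such as:

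*A function that could not be tested because of a device or communication fault counts as not successfully completed for that endpoint. A subject is left out of an endpoint only where the test was not done for a documented non-device reason. Exclusions are tabulated by endpoint and reason.*

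The cost is two or three sentences in the SAP and, if the CRF lacks one, a reason-not-done item. No extra subjects or visits are needed. There are three drawbacks: reported rates may be slightly lower, one fault may count against several endpoints, and sites must record why a test was not done. If no blocked test occurs, no result changes.

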# 2.10 Poolability Issue

No poolability analysis is planned for this clinical investigation.

# 2.11 Multiplicity Issues

Since there is no hypothesis testing in this study, no multiplicity adjustment will be considered.

# 2.12 Adjustments for Covariates

Unless otherwise specified, no adjustments for covariates will be made for any of the endpoint analyses.

# 2.13 Sensitivity Analysis

No sensitivity analysis is planned for this clinical investigation.

# 3.0 DESCRIPTIVE ENDPOINTS AND ADDITIONAL DATA

#### 3.1 **Baseline and Demographic Characteristics**

The following baseline and demographic variables will be summarized for the subjects enrolled: gender, medical condition indicated for MRI procedure and primary indication, etc.

# 3.2 Adverse Events

All the adverse events will be summarized descriptively for all subjects who are enrolled in this clinical investigation in terms the number of events and the percentage of subjects with events. The relationship with device (as determined by the Investigator), MRI procedure (as determined by the CEC) or COVID-19 (if applicable, as determined by the CEC) will be included.

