5.3.2 Inclusion Criteria

- 1. Subject or subject's legally acceptable representative must provide written informed consent prior to any clinical investigation related procedure.
- 2. Subject has been implanted, or is scheduled to be implanted, with a commercially available Infinity DBS system with MR Conditional labeling per locally approved indications for use.
- 3. Subject is scheduled to undergo a MRI procedure in compliance with the MRI Procedure Information Clinican's Manual. Anxiolytics and patient's regular medications may be administered, provided IFU criteria are met.
- 4. Subject is willing and able to comply with study requirements.

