5.4 Subject Enrollment

A patient is considered enrolled in the clinical investigation from the time the patient provides written informed consent.

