7.4 Adverse Event

7.4.1 Adverse Event Reporting

General AE Reporting

Safety surveillance and reporting starts as soon as the patient is enrolled in the clinical investigation. Safety surveillance and reporting will continue until the one month follow-up visit has been performed, the subject is deceased, the subject concludes participation in the clinical investigation or the subject withdraws from the clinical investigation, whichever comes first. All adverse event data will be collected throughout the time period defined above and will be reported to the Sponsor on a CRF. Additional information with regard to an adverse event should be updated within the appropriate CRF.

Unchanged, chronic, non-worsening or pre-existing conditions are not AEs and should not be reported.

An offline form will be made available to allow the investigator to report SAEs in the event the entry cannot be made in the electronic data capture (EDC) system. This does not replace the EDC reporting system. All information must still be entered in the EDC system as soon as feasible.

SAE Reporting

The investigator should report all SAEs to the Sponsor as soon as possible but no later than outlined below.

Clinical Site	Reporting timelines
All Sites	SAEs must be reported to the Sponsor no later than 3 calendar days from the
	day the site personnel became aware of the event or as per the site's local
	requirements, if more stringent than 3 calendar datys.

The date the site staff became aware the event met the criteria of an SAE must be recorded in the source document. The Investigator will further report the SAE to the local IRB/EC according to the local IRB/EC reporting requirements.

Reportable events to the sponsor are considered:

- All serious adverse events regardless of relatedness to the device and/or implant procedure
- All device- or implant procedure-related adverse events
- All MRI-related adverse events

Refer to the specific device manuals for the adverse events that are associated with implanting or using the neurostimulation system for DBS and for MRI related adverse events.

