#### 3.5 **Descriptive Endpoints or Additional Data**

- Additional safety endpoint: The frequency of all MRI-related adverse events will be reported as the number of occurrences of each event and the percentage of subjects experiencing each event in table format.
- Data (success or failure) for these outcomes will be summarized at post MRI Procedure visit
  - Rate of successful MRI mode 'turn on/off' functionality of the MRI mode
  - Rate of successful 'turn on/off' functionality for the stimulation
  - Rate of successful adjustments to the stimulation amplitude
  - o Rate of successful interrogation and download of the IPG parameters
  - Rate of successful ability to obtain lead impedance measurements

Rates will be reported as the percentage of subjects in which the device functionality could be successfully completed.

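### The SAP 3.2 adverse event summary takes its percentages over all consented subjects from consent onward, so its MRI-related percentages run slightly low and its other rows mix pre-scan with post-scan events

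*SAP*

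**What the plan says.** SAP 3.2 sets the population for the general adverse event summary: "All the adverse events will be summarized descriptively for all subjects who are enrolled". Results are event counts and percentages of subjects. The breakdowns it names are: "The relationship with device (as determined by the Investigator), MRI procedure (as determined by the CEC) or COVID-19", the last where applicable. It names no split at the scan, no split by configuration group, and no relationship to the implant procedure.

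Four protocol sections determine what that population and period contain:

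- Section 5.4: "A patient is considered enrolled in the clinical investigation from the time the patient provides written informed consent".
- Section 7.4.1: "Safety surveillance and reporting starts as soon as the patient is enrolled in the clinical investigation". The same section makes all serious events, all device- or implant-procedure-related events and all MRI-related events reportable.
- Section 5.3.2, second inclusion criterion: "Subject has been implanted, or is scheduled to be implanted". Implantation can therefore fall between consent and scan, and section 6.2 sets no minimum interval from implant to MRI.
- Section 5.8 allows 5% attrition after enrollment, for example "due to subject unwilling to undergo DBS implant procedure, or for any other reason". Section 8.1 also anticipates enrolled subjects who are never scanned.

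SAP 3.5 reports the additional safety endpoint, all MRI-related events, as "the number of occurrences of each event and the percentage of subjects experiencing each event in table format". It does not say which subjects form the denominator, and neither does protocol 8.2.3.

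**The concern.** A subject who is never scanned cannot have an MRI-related event. Including such subjects in the denominator lowers every MRI-related percentage in the SAP 3.2 summary. Collection from consent also brings events around implant surgery into the same rows as events after the scan. The investigator's assessment of relationship to the DBS procedure, which protocol 7.2 places on the case report form, is not among the breakdowns that SAP 3.2 names.

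The descriptive tables matter here because the primary endpoint is narrow. An event counts only if it is MRI-related and device-related, and is also either serious or the result of irrecoverable failure of therapy delivery or communication. Every other MRI-related event, such as a transient sensory disturbance during the scan, appears only in the summaries under SAP 3.2 and 3.5. Success is judged separately in the leads-only and full-system groups, yet neither section commits to showing events by group. A reader of the SAP 3.2 table could not tell from its stated content how many events followed the scan, or in which group.

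**Working it through.** **Inputs.** From protocol 5.8: at most 74 enrolled, about 35 per configuration group (70 in total), 5% attrition. From SAP 2.3.1: the event rate must be below 7% in each group.

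**Reproducing the enrollment figure.** 70 / (1 − 0.05) = 73.7, rounded up to 74. This agrees with the protocol.

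**Dilution in SAP 3.2.** The factor is scanned / enrolled = 70/74 = 0.946, so percentages are 4/74 = 5.4% lower in relative terms.

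| Subjects with an MRI-related event | Over 74 enrolled | Over 70 scanned | Difference (points) |
|---|---|---|---|
| 1 | 1.35% | 1.43% | 0.08 |
| 2 | 2.70% | 2.86% | 0.15 |
| 3 | 4.05% | 4.29% | 0.23 |

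If more subjects went unscanned than planned (assumption), three affected subjects would be 3/67 = 4.48% with 10% of 74 unscanned, or 3/59 = 5.08% with 20% unscanned, against 4.05% over all enrolled.

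**Mixing of periods.** The documents give no event risks, so all three inputs here are assumptions. Let r = 3% be the chance of any event after the scan, f the fraction of subjects implanted on study before the scan (25% to 100%), and q the chance of an implant-related event (2% to 10%). With independence, the percentage with any event over both periods is 1 − (1 − f·q)(1 − r).

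- f = 0.25, q = 0.02: 1 − 0.995 × 0.97 = 3.5%.
- f = 0.50, q = 0.05: 1 − 0.975 × 0.97 = 5.4%.
- f = 1.00, q = 0.10: 1 − 0.90 × 0.97 = 12.7%.

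All three compare with 3.0% after the scan. Mixing can therefore outweigh dilution, but only in the rows that are not restricted to MRI-related events.

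**Does the 7% decision move?** Protocol 8.2.1 limits the primary analysis to consented subjects who met the MRI eligibility requirements and had a study MRI. It counts only events during or after the MRI that the CEC finds MRI-related. SAP 2.3.1 applies the same event rule to the Primary Analysis Population. As a check, suppose the enrolled denominator were used by mistake, with 37 per group instead of 35:

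- Two subjects: 2/35 = 5.71% and 2/37 = 5.41%. Both are below 7%.
- Three subjects: 3/35 = 8.57% and 3/37 = 8.11%. Both are above 7%.

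Three affected subjects fall below 7% only when the group denominator reaches 43 (3/42 = 7.14%, 3/43 = 6.98%). The decision does not change at planned attrition.

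**The case against.** The strongest reply is that SAP 3.2 is an ordinary safety listing. Reporting every event from consent in everyone who consented matches the collection rule in protocol 7.4.1 and should be kept. The study question is answered elsewhere, by the primary endpoint and by a separate table of MRI-related events. The dilution is a fraction of a percentage point. CEC adjudication should keep pre-scan surgical events out of the MRI-related rows. The missing splits are read from silence, and SAP 2.2 mentions table mockups that are not part of the documents.

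Most of this stands, and it limits the point to one descriptive summary. It does not remove it. The denominator in SAP 3.2 is stated, not inferred, and it covers a summary that includes MRI relationship. CEC review of MRI relationship does not separate the periods in the all-event and device-related rows. A mockup may contain the splits, but the SAP text does not commit to them.

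A reader might also infer three stronger things, which the documents do not support:

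- That the rate deciding success is diluted or mixed. Protocol 8.2.1 restricts it to scanned subjects and to events during or after the MRI. The SAP's own population definition is partly blacked out, but the protocol text is intact.
- That SAP 3.5 uses the wrong denominator. It names none, which is a gap and not an error.
- That all four planned losses fall in the leads-only group, giving 2/39 = 5.1% against 2/35 = 5.7%. Protocol 5.8 offers implant refusal only as an example, without tying it to a group, and SAP 3.2 does not promise a table by group.

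**Conclusion.** The point holds for the SAP 3.2 summary and is minor. MRI-related percentages there are about 5% low in relative terms at planned attrition, less than 0.3 percentage points for up to three affected subjects. This assumes that 70 of 74 enrolled subjects are scanned. The all-event and device-related rows mix pre-scan and post-scan events. The size of that effect is unknown, and the range of 3.5% to 12.7% against 3.0% rests entirely on assumed risks. No conclusion about the 7% criterion changes. SAP 3.5 needs its denominator stated.

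**What to change.** Keep the listing of all events for all enrolled subjects. In SAP 3.2, add:

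- Percentages for MRI-related events and for all post-scan events over subjects who had a study MRI, by configuration group and in total.
- A split into two periods: consent to scan, and scan to the 1-month visit.
- The investigator's recorded relationship to the DBS procedure. A split at the scan is not enough by itself, because protocol 6.4.2 allows leads-only subjects to have an IPG implanted after the MRI, so surgical events can also fall in the second period.

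In SAP 3.5, state the same scanned denominator for the MRI-related event frequencies. Subjects who were scanned but did not meet the MRI eligibility requirements are outside the primary analysis. They were exposed and should stay in these safety tables.

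The cost is SAP wording and a table split. No new data are needed: the primary endpoint already requires event timing relative to the MRI, and protocol 7.2 already has the DBS-procedure relationship recorded where applicable.
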